## 10.9.2. Future PK and Biomarker Research

Any residual plasma and/or urine from PK sample collection will be stored by the Sponsor or bioanalytical facility for up to 3 years (or according to local regulations) after the closing of the study and may be used for future drug related research such as profiling of drug binding proteins, bioanalytical method development and validation purposes, stability assessments, metabolite assessments, or to assess other actions of the drug with plasma constituents. The analyses will only focus on analytes and/or additional biomarkers to further study the disposition and efficacy of APD418 and/or its mechanism of action. No disease/conditions, deoxyribonucleic acid (DNA) or ribonucleic acid (RNA) will be the focus of these analyses. Samples will not be submitted to a public database. The Sponsor and CROs involved in the clinical conduct and analyses of the samples/data will have access to the samples and/or the data that result from the analyses, if performed. At any time, the subjects can contact the clinical staff to request destruction of their residual samples after the required assessments are completed.

# 11. PLANNED STATISTICAL METHODS

## **11.1. General Considerations**

Details regarding the statistical analyses will be provided in the Statistical Analysis Plan (SAP), which will be finalized prior to database lock and unblinding.

Continuous variables will be summarized using the number of observations, mean, standard deviation (SD), median, minimum, and maximum. Categorical variables will be summarized using frequency counts and percentages.

Continuous variables measured at scheduled timepoints will be analyzed using a mixed-effects model with repeated measures (MMRM) method. The MMRM model will include treatment group, timepoint, interaction of treatment-by-timepoint, and randomization stratification factors as factors, and Baseline measure as a covariate. An unstructured covariance matrix will be specified for the MMRM model. Least square (LS) means at visit and LS mean differences between treatment group with p-values and corresponding 95% confidence intervals will be reported.

Unless otherwise specified, continuous endpoints will be analyzed using analysis of covariance (ANCOVA) with a model that includes treatment group and randomization stratification factors as factors, and Baseline CI value and other Baseline value as covariates. The LS means, standard errors (SE), and 95% confidence intervals for the treatments and their difference will be presented together with their p-values.

Categorical endpoints will be analyzed by either the Cochran-Mantel-Haenszel method, Fisher's exact test, or by logistic regression with a model that includes treatment group and randomization stratification factors as factors, and Baseline CI value and other and Baseline value as covariates. The odds ratio relative to placebo and percentage of difference from placebo will be presented together with corresponding 95% confidence intervals and the p-value.

Where statistical assumptions (eg, normality, proportional odds) are not met, alternative approaches will be evaluated (eg, non-parametric analysis, log transformation).

Efficacy data will be analyzed by randomized treatment, while safety data will be analyzed by actual treatment.

# **11.2.** Determination of Sample Size

Approximately 80 subjects are planned to be enrolled in this study (35 in Part A and 45 in Part B). It is assumed that CI, as measured with RHC, from Baseline to end of infusion is normally distributed with a mean of 2.0 and SD of 0.5. Sixty-five evaluable subjects (20 subjects in each of the 2 APD418 treatment groups and 25 in placebo) is sufficient to achieve at least 80% power to detect a treatment effect of 0.45 in favor of APD418 (a clinically significant improvement of 22.5% from placebo) between each of the APD418 treatment groups and placebo by a 2-sample t-test using a 2-sided significance level of 0.05.

The primary endpoint analysis will be based on pooled data from subjects in Part A and Part B. There will be 2 APD418 treatment groups of 20 subjects each (planned to consist of 5 subjects from Part A and 15 subjects from Part B) and one placebo treatment group of 25 subjects (planned to consist of 10 subjects from Part A and 15 subjects from Part B).

# 11.3. Stratification

In Part A, randomization will be stratified by Screening LVEF (> 25%,  $\leq$  25%). In Part B, randomization will be stratified by Screening LVEF (> 25%,  $\leq$  25%) and baseline carvedilol use (yes, no).

# 11.4. Analysis Sets

The primary and secondary endpoints will be analyzed using the Full Analysis Set (FAS) and safety endpoints will be performed using the Safety Set. For purposes of analysis, the following populations are defined (Table 3).

Analysis Set	Description
Full Analysis Set (FAS)	The FAS will include all randomized subjects, irrespective of whether they received any study treatment.
Modified Full Analysis Set (mFAS)	The mFAS will include all randomized subjects who receive any study treatment and have a baseline measurement and at least 1 post-baseline measurement. The mFAS is endpoint specific, therefore subjects included in the analysis set for one endpoint may differ from another endpoint, based on the baseline and post-baseline data.
Per Protocol Set	The Per Protocol Set will include all subjects from the FAS without major protocol violations that might affect the evaluation of the effect of study treatment on the primary endpoint.
Pharmacokinetic (PK) Set	The Pharmacokinetic Set will include all subjects in the Safety Set with at least 1 postdose PK measurement.
Safety Set	The Safety Set will include all randomized subjects who received at least one dose of study treatment.

# 11.5. Missing Data

Imputation strategies for the handling of missing data is described in detail in the SAP.

## **11.6.** Study Endpoints

#### 11.6.1. **Primary Endpoint**

Change in CI measured by RHC from Baseline to end of IV infusion at 6 hours

#### 11.6.2. Secondary Endpoints

Secondary endpoints are:

- Change in the following hemodynamic parameters measured by RHC from Baseline to end of IV infusion at 6 hours:
  - CO
  - PCWP
  - RAP
  - PAS/PAD
  - PAPi
  - SVR/SVRI
  - PVR
- Change in the following vital sign parameters from Baseline to end of IV infusion at 6 hours:
  - SBP
  - DBP
  - MAP
  - HR

- Change in the following hemodynamic and systolic function parameters measured by ECHO from Baseline to end of IV infusion at 6 hours:
  - SV
  - SVI
  - LVEF
  - FS
  - LVESV/LVEDV and diameter
  - LVGLS
  - LVGCS
- Change in hemodynamic (measured by RHC) and vital sign parameters listed above at intermediate timepoints during 6-hour IV infusion (during Dosing Period)
- Plasma and urine PK parameters of APD418
- Safety and tolerability of APD418 by incidence of all TEAEs

## 11.6.3. Pharmacokinetic Endpoints

PK endpoints are PK profiles of APD418, including, but not limited to, the following measures:

- Area under the concentration-time curve from time 0 to 6 hours (AUC0-6)
- Area under the concentration-time curve from time 0 to time of the last quantifiable plasma concentration (AUClast)
- AUC0-∞
- Cmax
- Terminal elimination half-life  $(t_{1/2})$
- Distribution half-life  $(t_{1/2\alpha})$
- Time to maximum observed plasma concentration (tmax)
- CL
- Volume of distribution based on the terminal phase (Vdz)
- Volume of distribution at steady state (Vdss)
- Mean residence time from time 0 to time of last quantifiable plasma concentration (MRTlast)
- Average plasma concentration during dosing interval (Cave)
- Renal clearance (CLr)

## 11.6.4. Exploratory Endpoints

Exploratory endpoints are:

- Change in hemodynamic parameters (measured by RHC) listed above at 1 hour after the end of 6-hour IV infusion (during Postdose Period)
- Change in vital sign, hemodynamic (measured by ECHO), and cardiac systolic function (measured by ECHO) parameters listed above for 18 hours after end of 6-hour IV infusion (during Postdose Period)
- The relationships between select APD418 plasma exposure measures and change in select PD parameters
- The relationships between select subject/disease characteristics (eg, Baseline LVEF, Baseline CI, Baseline SBP, duration of HFrEF, renal function, concomitant medications) and change in select PD parameters
- Change in markers of renal function (eGFR, BUN, cystatin C, urine protein/creatinine ratio, urinary sodium excretion)
- Change in cardiac biomarkers (NT-pro-BNP, hs-cTnT)
- Change in the following additional systolic and diastolic function parameters measured by ECHO: E, A, E', S', E/A E/E' ratio), TAPSE, tricuspid regurgitation (TR) velocity, and LA volume index
- Change in urine output
- Change in body weight
- The OATP genotype

#### 11.6.5. Safety Endpoints

• Safety and tolerability of APD418 by incidence of all TEAEs

## **11.7. Testing Strategy**

No formal testing strategy or adjustments of the Type I error will be employed for secondary or exploratory endpoints. Estimates and confidence intervals for treatment groups and from pairwise comparisons will be used in an exploratory manner.

## **11.8.** Interim Analysis

No formal interim analysis of efficacy is planned..

## **11.9. Dose Escalation and Dose Selection**

After treatment of each cohort in Part A, an assessment of the safety/tolerability and PK data will be performed by the dose escalation committee (blinded data review by the Sponsor and Investigator representatives) prior to dose escalation to the next dose level in Part A. The decision to escalate to the next planned dose level in Part A will be made with consideration of

the safety-related dose escalation stopping criteria and overall safety (including AEs, clinical laboratory, and vital sign/ECG data) and PK data of each cohort, as described in Section 10.6.2.

Doses for each subsequent cohort in Part A may be adjusted depending on the safety, tolerability, and PK results of previous cohort(s). The maximum dose in the study will not exceed 2 mg/kg/h (12 mg/kg) and will not produce exposures to APD418 higher than that predicted for a 12 mg/kg dose (ie,  $C_{max}$  of 5700 ng/mL or AUC0- $\infty$  of 39,000 ng·h/mL) without a protocol amendment.

The dose escalation committee may decide to evaluate an alternative dose(s) in the subsequent cohort(s) in Part A in the following scenarios:

- Based on the safety profile observed, lower or higher than planned dose(s) may be chosen to be evaluated in the subsequent cohort(s) (not to exceed 12 mg/kg without a protocol amendment)
- If large deviations from the expected PK profile are observed, adjustment to the planned dose escalations may occur to ensure evaluation of dose levels that will elicit appropriate exposure
- If warranted based on the emerging safety and PK data, up to 1 additional or 1 fewer cohort may be studied than originally planned

At the conclusion of Part A, the dose selection committee will perform a safety/tolerability and PD data assessment to identify 2 doses to be expanded in Part B (unblinded review of Part A data by the Sponsor representatives who are not directly involved in study conduct; site staff, and sponsor representatives involved in study conduct will remain blinded throughout the study). Selection of doses will be based on the criteria including, but not limited to:

- Doses selected for expansion in Part B have shown a favorable safety profile in Part A as determined by the criteria described in Section 10.6.2
- Doses selected for expansion in Part B have shown clinically relevant PD effects indicating a clinically meaningful benefit in cardiac function (eg, SV, CO, LVEF)

Sample size for Part B may also be adjusted based on data review of Part A. The sample size will not increase by more than approximately 15% of the sample size without a protocol amendment.

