Each subject will receive a single dose of study treatment as an IV infusion over a duration of 6 hours. The initial APD418 dose to be studied in the first cohort of Part A will be 0.17 mg/kg/h (total dose 1 mg/kg). After 7 subjects have completed treatment in each cohort in Part A, an assessment of the safety/tolerability and PK data will be conducted by the dose escalation committee (blinded data review by the Sponsor and Investigator representatives) to determine whether dose escalation to the next dose level in Part A can occur. Doses for each subsequent cohort in Part A may be adjusted depending on the safety, tolerability, and PK results of previous cohort(s). The maximum dose in the study will not exceed 2 mg/kg/h (12 mg/kg) without a protocol amendment. At the conclusion of Part A, the dose selection committee will perform safety/tolerability and PD data assessment to identify 2 APD418 doses to be expanded in Part B (unblinded review of Part A data by the Sponsor representatives who are not directly involved in study conduct; site staff and sponsor representatives involved in study conduct will remain blinded throughout the study). Additional details about the dose escalation and the dose selection process are described in Sections 10.6.2 and 11.9. Additional subjects and/or cohorts may be enrolled in the study as described in Sections 6.4 and 11.9. The sample size will not increase by more than approximately 15% without a protocol amendment.

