## Statistical methods:

Determination of sample size:

Approximately 80 subjects are planned to be enrolled in this study (35 in Part A, 45 in Part B).

It is assumed that baseline CI, as measured with RHC, is normally distributed with a mean of 2.0 and a standard deviation (SD) of 0.5. Sixty-five evaluable subjects (20 subjects in each of the 2 APD418 treatment groups and 25 in placebo) is sufficient to achieve at least 80% power to detect a treatment effect of 0.45 in favor of APD418 (a clinically significant improvement of 22.5% from placebo) between each of the APD418 treatment groups and placebo by a 2-sample t-test using a 2-sided significance level of 0.05.

The primary analysis will be based on pooled data from subjects in Part A and Part B. There will be 2 APD418 treatment groups of 20 subjects each (planned to consist of 5 subjects from Part A and 15 subjects from Part B) and 1 placebo treatment group of 25 subjects (planned to consist of 10 subjects from Part A and 15 subjects from Part B).

A blinded review of the data to evaluate the assumption regarding the SD of the change in CI may be conducted. The planned sample size will not be reduced as a result of the sample size re-estimation. Details will be specified in the Statistical Analysis Plan (SAP).

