## Dose Escalation and Dose Selection:

After treatment of each cohort in Part A, an assessment of the safety/tolerability and PK data will be performed by the dose escalation committee (blinded data review by the Sponsor and Investigator representatives) prior to dose escalation to the next dose level in Part A. Doses for each subsequent cohort in Part A may be adjusted depending on the safety, tolerability, and PK results of previous cohort(s).

At the conclusion of Part A, the dose selection committee will perform a safety/tolerability and PD data assessment to identify 2 doses to be expanded in Part B (unblinded review of Part A data by the Sponsor representatives who are not directly involved in study conduct; site staff and sponsor representatives involved in study conduct will remain blinded throughout the study).

Additional details about the dose escalation and the dose selection process are described in Sections 10.6.2 and 11.9.

Additional subjects and/or dose cohorts may be enrolled in the study as described in Sections 6.4 and 11.9.

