Each subject will receive a single dose of study treatment as an IV infusion over a duration of 6 hours. The initial APD418 dose to be studied in the first cohort of Part A will be 0.17 mg/kg/h (total dose 1 mg/kg). After 7 subjects have completed treatment in each cohort in Part A, an assessment of the safety/tolerability and PK data will be conducted by the dose escalation committee (blinded data review by the Sponsor and Investigator representatives) to determine whether dose escalation to the next dose level in Part A can occur. Doses for each subsequent cohort in Part A may be adjusted depending on the safety, tolerability, and PK results of previous cohort(s). The maximum dose in the study will not exceed 2 mg/kg/h (12 mg/kg) without a protocol amendment. At the conclusion of Part A, the dose selection committee will perform safety/tolerability and PD data assessment to identify 2 APD418 doses to be expanded in Part B (unblinded review of Part A data by the Sponsor representatives who are not directly involved in study conduct; site staff, and sponsor representatives involved in study conduct will remain blinded throughout the study). Additional details about the dose escalation and the dose selection process are described in Sections 10.6.2 and 11.9. Additional subjects and/or cohorts may be enrolled in the study as described in Sections 6.4 and 11.9. The sample size will not increase by more than approximately 15% without a protocol amendment.

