# 6. STUDY TREATMENT

## 6.1. Study Treatment(s) Administered

Study treatments in this study include the pharmaceutical form of the active substance being tested (APD418), and the volume-matched placebo being used as a reference (reference therapy). Study treatment(s) are listed in Table 1.

The subject weight recorded during Predose Period on Day 1 will be used to calculate the study treatment dose.

Study Treatment	Dose(s) a	Mode of Administration	Frequency	Formulation
APD418 (Part A: Cohort 1)	0.17 mg/kg/h (1 mg/kg)	IV infusion	Single 6-hour IV infusion	IV formulation
APD418 (Part A: Cohort 2)	0.50 mg/kg/h (3 mg/kg)	IV infusion	Single 6-hour IV infusion	IV formulation
APD418 (Part A: Cohort 3)	1.0 mg/kg/h (6 mg/kg)	IV infusion	Single 6-hour IV infusion	IV formulation
APD418 (Part A: Cohort 4)	1.5 mg/kg/h (9 mg/kg)	IV infusion	Single 6-hour IV infusion	IV formulation
APD418 (Part A: Cohort 5)	2.0 mg/kg/h (12 mg/kg)	IV infusion	Single 6-hour IV infusion	IV formulation
APD418 (Part B: Dose Group 1)	X mg/kg/h	IV infusion	Single 6-hour IV infusion	IV formulation
APD418 (Part B: Dose Group 2)	Y mg/kg/h	IV infusion	Single 6-hour IV infusion	IV formulation
Placebo (Part A and Part B) b	NA	IV infusion	Single 6-hour IV infusion	IV formulation

Table 1:Proposed Study Treatment(s)

a After treatment of each cohort in Part A, a blinded safety/tolerability and PK data assessment will be conducted by the dose escalation committee to determine whether dose escalation to the next dose level in Part A can occur. Doses for each subsequent cohort in Part A may be adjusted depending on the safety, tolerability, and PK results of previous cohort(s). At the conclusion of Part A, the dose selection committee will perform an unblinded safety/tolerability and PD data assessment to identify 2 APD418 doses to be expanded in Part B. Additional cohorts (to study intermediate or higher doses) and/or additional subjects may be enrolled in the study based upon data reviews from the prior cohorts.

b Placebo will follow the same dilution instructions to match the volume of APD418 in the same cohort and mode of administration will match that of APD418.

IV, intravenous; NA, not applicable

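### Does the open-ended wording on adjusting Part B's sample size in Section 11.9 need to be tightened?

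*Combined protocol and SAP*

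**What the plan says.** Two places deal with changing the sample size.

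- **Synopsis, Statistical methods.** "A blinded review of the data to evaluate the assumption regarding the SD of the change in CI may be conducted". The text adds that "The planned sample size will not be reduced as a result of the sample size re-estimation" and leaves the details to the SAP. Section 11.2, the matching section in the body, gives the same sample size but omits this review.
- **Section 11.9.** After describing the unblinded dose-selection review of Part A, it says "Sample size for Part B may also be adjusted based on data review of Part A". The limit follows: "The sample size will not increase by more than approximately 15% of the sample size without a protocol amendment".

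The same limit appears in the synopsis under Study Design ("The sample size will not increase by more than approximately 15% without a protocol amendment"), in Section 3.1 and in Section 6.4.

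Other sections describe what this flexibility is for. Section 3.1 says "Additional subjects and/or cohorts may be enrolled in the study as described in Sections 6.4 and 11.9", and the synopsis paragraph on dose escalation and selection says "Additional subjects and/or dose cohorts may be enrolled in the study as described in Sections 6.4 and 11.9". Footnote a to Table 1 in Section 6.1 says that "additional subjects may be enrolled in the study based upon data reviews from the prior cohorts".

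Section 11.2 pools Part A and Part B for the primary analysis: 5 + 15 subjects at each selected dose and 10 + 15 on placebo.

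**The concern.** Read alone, the Section 11.9 sentence leaves four things open.

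1. **Blinding.** It follows a review in which the dose selection committee sees unblinded pharmacodynamic data. One could infer that this committee may also resize Part B knowing the treatment effects. Part A subjects stay in the pooled primary test, and Section 11.8 plans no formal interim efficacy analysis, so that could bias the test.
2. **Direction.** Only increases are limited. The no-reduction sentence in the synopsis is tied to the blinded re-estimation, so a cut under Section 11.9 is not expressly ruled out. A large enough cut would break the claim of at least 80% power.
3. **Cap base.** The 15% could be of the planned 80 or of Part B's 45.
4. **Link.** Nothing says whether the Section 11.9 adjustment is the blinded review in the synopsis or a second mechanism. The SAP that was to give details remained in draft (v0.4, per the biostatistics Note to File), and its text is not available.

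**Working it through.** **Inputs** (Section 11.2): difference 0.45, SD 0.5, two-sided 0.05, two-sample t-test, 20 per dose against 25 placebo. Section 11.9 allows one Part A cohort more or fewer. Each cohort has 5 active and 2 placebo subjects.

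**The plan's own figure.** The noncentrality is 0.45 / (0.5 × √(1/20 + 1/25)) = 0.45 / 0.15 = 3.00, with 43 degrees of freedom and a critical value of 2.017. Power is 83.5%, so the stated figure of at least 80% is confirmed.

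**Effect of changing Part B.** With m subjects per Part B arm, the comparison is (5 + m) against (10 + m):

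| m | Groups | Power |
|---|---|---|
| 13 | 18 vs 23 | 79.6% |
| 14 | 19 vs 24 | 81.6% |
| 15 (planned) | 20 vs 25 | 83.5% |
| 17 | 22 vs 27 | 86.6% |
| 19 | 24 vs 29 | 89.2% |

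With one fewer Part A cohort, Part A gives 8 placebo subjects instead of 10. Power is then 82.0% at m = 15, 80.0% at 14 and 77.9% at 13.

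**Cap base.** 0.15 × 80 = 12, which is 4 per Part B arm if all go there (m = 19). 0.15 × 45 = 6.75, which is 6 subjects at 1:1:1, or 2 per arm (m = 17). An extra Part A cohort of 7 would leave 12 − 7 = 5 under the study-wide cap. That is 1 per arm, 21 against 28, with power 86.3%. This last case is not a third base; it is the study-wide cap with the cohort counted.

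**Type I error if Part B were resized with effects known.** Take one dose, a z-test with known SD and a one-sided nominal level of 2.5%. Given the Part A means, choose the m that maximises the chance of rejection under the null. This is a worst case that no real rule would match.

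| Permitted m | One-sided error |
|---|---|
| 15 only | 2.50% |
| 15–16 | 2.53% |
| 15–17 | 2.56% |
| 15–19 | 2.62% |
| 10–19 (assumed floor) | 2.84% |
| 5–19 (assumed floor) | 3.23% |

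The floors of 10 and 5 are assumptions; the documents contain neither. Dose selection is left out of these figures.

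**Effect of covariate adjustment.** The primary analysis is a repeated-measures model adjusted for Baseline CI, not the planning t-test. Assume that 0.5 is the unadjusted SD of the change and that its correlation with the covariate is 0.3; the documents give no value. The residual SD is 0.5 × √(1 − 0.09) = 0.477. Power is then 83.2% at m = 13 and 81.2% at m = 12.

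**The case for a change.** The strongest case for a change is that the two mechanisms differ in kind. The synopsis review is blinded. The only Part A review in Section 11.9 that includes pharmacodynamic data is unblinded, and the word *also* can be read as giving that committee the sample size as well. A few sentences would settle it at no cost in patients. The cap base can matter too. At an assumed SD of 0.55, power is 76.0% as planned, 79.7% with 17 per Part B arm and 82.9% with 19, so the reading chosen decides whether 80% can be recovered.

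The silence in Section 11.9 and the omission from Section 11.2 stand. The consequences are small. Adding subjects after seeing Part A effects moves the error by about 0.1 percentage point at most. The cap example turns on 3.2 points of power under an SD that the plan does not assume, with a cap worded as approximate and open to amendment. The context in Section 3.1, enrolling more subjects in the study, favours the planned total of 80.

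Barring the committee from setting the size, fixing a floor of 15 per arm, or requiring a combination test would be design choices. A combination test is out of proportion to the inflation found. None of these would address the larger matter of selecting doses on Part A data and then pooling those data, which is a separate point. So is the SD label: the synopsis attaches 0.5 to baseline CI, and Section 11.2 attaches it to CI from Baseline to end of infusion.

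**Conclusion.** No change is needed. The synopsis and Section 11.9 leave detail unstated but do not contradict each other, and an increase within a study-wide cap is the natural reading. Followed that way, the plan keeps its stated power (83.5% as planned, up to 89.2% at 19 per Part B arm), and the one-sided error is at most 2.62% against 2.5%. Harm would need either a cut of two or more per Part B arm, which no section proposes and which misses 80% by only 0.4 point at 79.6%, or assumed floors of 10 or 5 per arm with the size chosen to favour rejection. With one fewer Part A cohort, the same two-per-arm cut gives 77.9%.

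These figures rest on the plan's difference of 0.45 and SD of 0.5, on the t-test for power and a known-SD z-test for error, and on one dose at a time without dose selection. The unavailable draft SAP may have filled the gap, but that cannot be checked. Nothing indicates that either provision was used: enrollment was terminated, and the biostatistics Note to File plans outputs for Part A Cohorts 1 and 2 only.
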